#### 8.3.6 Blood samples (5 minutes) - BASELINE AND FOLLOW-UP

Biomarkers that can be quantified from peripheral tissue (such as plasma, blood cells or hair) are promising indicators of the pathophysiological processes that underlie mental disorders. For this study, we selected blood biomarkers with an established association with psychotic symptoms and / or 5-HT4R agonism whilst also minimising participant burden, and limiting the invasiveness of specimen collection.

## 8.3.7 Optional Microbiome analysis (collection to take place at home) (5 minutes) – BASELINE AND FOLLOW-UP

Proof of concept to measure uptake and acceptability of optional microbiome analysis. 5-HT4 agonists, as drugs with action of gut receptors, may impact on the human microbiome.

#### 8.3.7 Discussion re study and intervention (5 minutes) – BASELINE AND FOLLOW-UP

At baseline / Study Visit 2, participants will receive their study medication and confirmation of instructions on how to take this. There will be an opportunity to ask questions.

At follow up / Study Visit 3, there will be an opportunity for participants to ask questions about the study and to give feedback on the process.

UOB ethics number: ERN\_3117

#### 8.4 Duration of assessments

Screening (may be conducted online or in person): lasts 1 hour

Baseline assessment: lasts approximately 2 hours (includes MRI scan time with preparation)

Follow-up assessment: lasts approximately 2 hours (includes MRI scan time with preparation)

#### 8.5 Outcomes

Primary: The effect of 7-10 days' prucalopride versus placebo on neurocognitive task performance.

Secondary include: Prucalopride's effects on subjective cognition, other measures (including mood/anxiety symptoms), task and resting state functional connectivity (cognitive versus affective networks). Blood samples will allow subsequent association of responders with biomarkers and drug levels.

#### 8.6 Participant remuneration

Participants will receive £100 for completing the study, and up to £25 for travel expenses throughout the study. Ineligible participants at screening or participant withdrawals before the end of the study will receive £10 remuneration.

## 9. Randomisation and Blinding

Drug procurement, & encapsulation will be carried out by an approved external provider sourced through the University of Birmingham: the NHS Scotland Pharmaceutical 'Specials' Service.

The Encapsulation Lead / Regulatory Manager from the Oxford Health Biomedical Research Centre will generate a randomisation list using Sealed Envelope; https://www.sealedenvelope.com (an online randomisation tool established since 2001; ISO 27001 compliant and accredited by UKAS). The University of Birmingham is a partner of the OHBRC and therefore as such is able to make use of their facilities and resources. Sealed Envelope is a well established web-based randomisation tool that has been used and cited in numerous peer-reviewed papers, including a published experimental medicine study by this proposed study's PI ([name] et al., The effect of the 5-HT4 agonist, Prucalopride, on functional magnetic resonance imaging faces task in the healthy human brain. Frontiers Psychiatry (2022) 13:859123). The list will be randomised against 2 treatment groups (placebo vs drug) and stratified according to gender (male vs female). Randomisation will be blocked in design (Blocks of 4) to ensure even distribution of treatment allocations for every 4 stratified participants.

Drug & placebo encapsulation and labelling will subsequently be carried out using this randomisation list according to the NHS Scotland Pharmaceutical 'Specials' Service SOP signed by a Qualified Person (QP). In summary, drug tablets and placebo are over-encapsulated in matched capsules. This is led by their Encapsulation Lead and carried out by 2 people such that each part of the encapsulation process is double checked. Encapsulation is carried out on 'clean' benches in designated rooms, by personnel wearing PPE to prevent contamination of the encapsulated drugs. Correct number of either prucalopride or placebo capsules are counted into labelled bottles according to the blinded randomisation list. Bottles are labelled numerically with gender identifiers e.g. F01, F02 for the first two female participants, M01, M02 for the first male

UOB ethics number: ERN\_3117

participants. Thus labelling with these unique identifiers enable the capsule contents to remain blinded to the participants and study personnel.

The unblinded randomisation code list will be kept securely in a password protected file on a secure server at Oxford University (Encapsulation Lead has access). In the event of an emergency where unblinding is necessary, an emergency medic has been identified at Birmingham who will hold a password protected copy of this list. This document will be emailed from the Encapsulation Lead to the emergency medic before recruitment starts. The Encapsulation Lead will also hold a copy of the unblinded list at Oxford and study personnel will have been notified ahead of recruitment about her contact details. The Study PI ([name]) will ensure that emergency contacts for participants are available at the time participants are taking the treatments.

Blinded study staff at Birmingham will receive the labelled bottles of drug/placebo capsules securely from the external encapsulation provider, and these will be stored in a locked medicine cabinet in Birmingham and Solihull Mental Health Trust Pharmacy. Bottles will be allocated to participants in numerical order by a study clinician and a record kept.

Experimental medicine studies using drugs that are not CTIMPs, such as this one, do not need to adhere to clinical trial regulations including those associated with treatment/drug preparation. However, the Encapsulation Lead has also carried out Good Manufacturer training, and all staff at NHS Scotland Pharmaceutical 'Specials' Service adhere to Good Manufacturing Practice.

The encapsulation group at Oxford has a number of years experience with preparing randomisation lists for experimental medicine studies that have been approved by University of Oxford Ethics committees. The BRC Depression Therapeutics Theme will fully support [name] with this study and offer any support and advice throughout the study as needed. Integrity of the blind and code break will be confirmed at the end of the study by asking for participant feedback on randomisation guesses. All documentation relating to randomisation and blinding, will be archived along with the rest of the TMF at the end of the research project. See 16.3.6 Data Archiving for further information.

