## 12. Risk Mitigation

A project-specific risk assessment has been performed and is documented below as per Standard Operating Procedure (UoB SOP PROJECT OVERSIGHT & QUALITY MANAGEMENT: UoB-POS-SOP-001, V3.0, 8.1.2024).

- Risk: Potential for insufficient recruitment from the community
   Mitigation: We have allowed additional time (3 months) for recruitment in our study plan to allow for
   slower recruitment in some months (estimated 1-2 participants per months after data collection
   starts). We are also co-producing recruitment materials with specifically recruited Birmingham YAG
   members to ensure that our participant-facing materials are as inclusive as possible and are attractive
   to the community.
- Risk: It is possible that some participants may find it difficult to understand instructions regarding study processes.
   Mitigation: We will give these both verbally and in written form, and will check understanding prior to study procedures.
- 3. Risk: It is possible that participants may have varying sub-clinical cognitive and mood differences at recruitment, which may impair our ability to detect signal in neurocognitive measures.

UOB ethics number: ERN 3117

Mitigation: We will assess baseline mood and subjective cognitive difficulties, and we can incorporate these into analytical models as necessary to account for subclinical differences in cognition and mood.

[figure not shown]
- 4. Risk: Participants may deteriorate in terms of mental state during the course of the study. Mitigation: As the study is short, and involves only healthy volunteers, this is unlikely to occur. However, we will monitor the results of the SCID at screening, and the PHQ-9, GAD-7 and PLE during each study visit. Any concerns will be discussed with the PI and / or supervising medical investigators, all of whom are psychiatrists with experience in managing patients with serious mental illness and suicidal thoughts and behaviours. We will also ask all participants to provide the details of a GP or other health professional so that the study team can advise them of their participation in the study
- 5. Risk: Bias from accidental unblinding Mitigation: To preserve the blind, prucalopride and placebo will be encapsulated to appear identical and labelled blinded. The randomisation list will be generated by an independent pharmacist and access to the unblinded code list will be restricted to the randomisation service provider.

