#### 15.2 Monitoring and auditing

Study monitoring will be performed in accordance with applicable regulations, ICH-GCP, and University of Birmingham Standard Operating Procedures (SOPs). An audit is a systematic and independent examination of study-related activities and documents to determine whether the approved study-related activities were conducted, and the data were recorded, analysed and accurately reported according to the protocol, SOPs and any applicable institutional requirements.

The Investigators will ensure that direct access to source data / documents for the purposes of monitoring, audits, ethics review and regulatory inspections is available throughout the study and during the record retention period. In addition, the PI will ensure that each study participant has consented, in writing, to their records being available for monitoring audits and regulatory inspections.

Considering the small sample size over a single site, it will be appropriate to monitor the study as follows: At each three-four monthly Study Management Group meetings the following aspects of the study will be reviewed and minuted.

[figure not shown]
- Numbers and completeness of case report form (eCRF)
- Compliance with the protocol's treatment according to participant report
- Any adverse event report form completed
- Any notification of protocol deviations
- Any concerns regarding quality of data

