## Data Management

#### 16.1 Sample size calculation

Previous studies investigating the effect of prucalopride / other serotonergic drugs on acute cognition assessed with behavioural measures indicate an effect size of 0.8-0.9 may be expected. As relatively little is known about 5-HT4R stimulation in healthy participants we PLEs, we conservatively estimated a smaller effect size (0.5-0.7) for sample size calculation. This indicates 15-17 participants/group would give 85-90% power to detect a significant group difference at a 0.05 false positive rate. We aim to recruit up to 36 (18 in each group) to allow for withdrawals and exclusions for data quality reasons.

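### Section 12 limits the unblinded code list to the randomisation provider, but section 9 gives a full copy to a medic at the trial site, so one emergency would show that person every allocation

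*Protocol*

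**What the plan says.** **Who holds the code.** Section 9 of the protocol keeps the unblinded list in a password-protected file at Oxford, where the Encapsulation Lead has access. For emergencies it adds that "an emergency medic has been identified at Birmingham who will hold a password protected copy of this list". The copy is emailed before recruitment opens. The Encapsulation Lead is a second contact, and study personnel receive those contact details in advance. Section 12, listing mitigations for accidental unblinding, says that "access to the unblinded code list will be restricted to the randomisation service provider".

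**Who makes the list.** Section 9 gives this to the Encapsulation Lead / Regulatory Manager at the Oxford Health Biomedical Research Centre, using an online tool. Section 12 gives it to an independent pharmacist.

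**How the list is built and used.** There are two arms and two strata, male and female, defined by gender. "Randomisation will be blocked in design (Blocks of 4) to ensure even distribution of treatment allocations for every 4 stratified participants". "Bottles are labelled numerically with gender identifiers e.g. F01, F02 for the first two female participants", with M numbers for men. "Bottles will be allocated to participants in numerical order by a study clinician and a record kept". Section 15.2 confirms one site ("Considering the small sample size over a single site"), and section 16.1 gives the size: "We aim to recruit up to 36 (18 in each group) to allow for withdrawals and exclusions for data quality reasons".

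**What protects the blind.** Capsules are matched (sections 9 and 12), and section 9 describes the Birmingham staff who receive the bottles as blinded.

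**The concern.** The restriction in section 12 is one of the safeguards the plan offers against accidental unblinding. If section 9 is followed, that safeguard does not exist as described: someone outside the randomisation provider, at the only trial site, holds the complete code from before the first participant is enrolled. The only Birmingham mechanism described is a single file, so a justified code break for one participant also discloses everyone else's allocation to the person who opens it.

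What is at stake depends on that person's other duties, which the protocol does not give. Part of the primary outcome depends on contact with staff: section 8.3.5 has the verbal learning list read aloud to participants. Section 9 checks the blind through participants' guesses and mentions no guesses by staff, so knowledge on the staff side could go unnoticed.

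The block design is a lesser worry. With one published block size and labels that run in list order within gender, anyone who sees a bottle number knows its place in the block (F01 to F04 is the first block for women). If side effects hint at earlier allocations, that knowledge carries forward to later ones.

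**Working it through.** **1. Code access, side by side**

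| Item | Section 9 | Section 12 |
|---|---|---|
| Generates the list | Encapsulation Lead / Regulatory Manager, Oxford | Independent pharmacist |
| Can see the unblinded list | Encapsulation Lead, and an emergency medic at Birmingham | Randomisation service provider only |
| Form of the emergency copy | One password-protected copy of the list | Not described |

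The access row cannot be reconciled. Whether the provider is taken to be the Oxford group or the online tool, a Birmingham medic is neither.

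**2. Exposure from one code break.** One allocation is needed. The file shows up to 36, so up to 36 − 1 = 35 are disclosed without need, to one person.

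**3. Predictability from blocks of 4.** The protocol states no figure, so there is none to reproduce. A block holds two of each arm in one of 6 equally likely orders.

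*All earlier allocations in the block known.* The chance of a correct best guess is:
- position 1: 1/2
- position 2: 2/3
- position 3: 1/3 × 1 + 2/3 × 1/2 = 2/3 (certain only when the first two match, probability 1/3)
- position 4: 1

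Mean = (0.500 + 0.667 + 0.667 + 1) / 4 = 70.8%. The share that is certain is (1/3 + 1) / 4 = 33.3%, or about 12 of 36 if all blocks are complete.

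*Earlier allocations only inferred, each with accuracy q.* The protocol gives no q, so it is an assumption. The best guess is correct with probability:
- position 1: 1/2
- positions 2 and 3: (1 + q) / 3 each
- position 4: q² + 2q(1 − q)²

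| q | Position 1 | Positions 2 and 3 | Position 4 | Mean |
|---|---|---|---|---|
| 0.5 (blind intact) | 0.500 | 0.500 | 0.500 | 50.0% |
| 0.6 | 0.500 | 0.533 | 0.552 | 53.0% |
| 0.7 | 0.500 | 0.567 | 0.616 | 56.2% |
| 0.8 | 0.500 | 0.600 | 0.704 | 60.1% |
| 0.9 | 0.500 | 0.633 | 0.828 | 64.9% |
| 1.0 (all known) | 0.500 | 0.667 | 1.000 | 70.8% |

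*After one genuine code break.* If one member of a block is known, two of the other three are on the opposite arm, so each is there with probability 2/3. A participant-level break therefore still leaks a little when the block size is known.

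**4. What varying the block size buys.** In 40,000 simulated lists of 18 (an even gender split, assumed), a guesser who knows every earlier allocation and follows the running imbalance is right 69.5% of the time with fixed blocks of 4 and 68.4% with random blocks of 4 and 6. The first figure is below 70.8% because 18 is not a multiple of 4. The gain is about 1 percentage point. The price is balance: an unfinished block can leave the arms apart by half its size, 2 for a block of 4 and 3 for a block of 6.

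**5. Strata.** Section 8.1 collects sex and gender separately at screening. Section 9 stratifies on gender with two levels, so a participant recorded as neither male nor female has no stratum and no bottle series.

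**The case against.** The best defence is that the blind is well protected in practice. Capsules match, receiving staff are blinded, and the medic is described separately from them with no recruiting, dispensing or testing role. An emergency could also go through the Encapsulation Lead, who could release one allocation without the Birmingham file being opened. All of this stands, and it limits the harm. It does not make section 12 true, and separate mention is not a statement of independence.

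A reader might infer that one emergency would unblind the trial. The protocol does not support that: the file would be seen by whoever opens it.

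A reader might also infer that blocks of 4 make allocation guessable, with 12 of 36 certain. That figure presumes every earlier allocation is already known, which means the blind has already failed. With the blind intact, prediction stays at 50%. Section 11 reports that this titration was well tolerated in earlier work, which points to weak cues if anything. A side effect that reveals a participant's arm does so directly, whatever the block size. Nor does the protocol say that the team controls enrolment order; section 8.3.3 ties visit timing to participants' schedules.

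A route for leakage does exist. The drug acts on the gut (section 8.3.7), the study team checks in on days 2 and 4 (section 11), and recruitment of one or two participants a month (section 12) against 7 to 10 days of treatment means that earlier experiences will usually be known before the next bottle is used. That justifies a secondary remark and no more.

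Finally, the independent pharmacist and the Encapsulation Lead could be the same person, so that difference may be one of wording only.

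**Conclusion.** The point holds, as a minor one that is cheap to put right. The protocol contradicts itself on access to the unblinded list, and its stated safeguard is untrue as written. With no participant-level break described, one use of the Birmingham copy would disclose up to 36 allocations to one person at the site whose independence is not stated. This rests on the text alone and on the planned recruitment of 36.

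The block-size element is secondary and conditional. It adds about 3 to 10 percentage points to the chance of a correct guess if earlier allocations are inferred with 60% to 80% accuracy, a range that is assumed, and nothing if the blind holds. The missing stratum is a small operational gap.

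**What to change.** Before bottles are labelled, in this order:

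1. Replace the full list at Birmingham with participant-level code breaks, either sealed or as single-record electronic access, so that one emergency reveals one allocation. State whether the medic has any part in recruitment, dispensing or assessment.
2. Rewrite the mitigation in section 12 to agree with section 9 on who generates the list and on everyone who holds it.
3. As a small extra, vary the block sizes and keep them in a restricted document outside the protocol.
4. Stratify on sex, already collected at screening, or otherwise make sure that every participant has a stratum and a bottle series.

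Items 1 and 2 cost a change in the form of the code break and some wording. Items 3 and 4 are list settings, and item 3 may leave slightly more imbalance within a stratum. If bottles have already been labelled, items 1 and 2 can still be made without touching the list.

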#### 10. Intervention

#### 9.1 Prucalopride

Name of drug/substance to be used	Prucalopride
Formulation and route of administration for study	1mg prucalopride tablets will be encapsulated in opaque capsules.
Dose and route of administration for study	1mg oral dose daily for 2 days, then 2x1mg oral dose daily for 5-8 days
Duration of treatment for study	Seven to ten days
Licence status of this drug/substance	Prucalopride is a licensed drug.
Usual Indication	Prucalopride is indicated for the symptomatic treatment of chronic constipation in adults.
Usual Dose	The usual dose given is 2 mg once daily with or without food, at any time of the day.

[figure not shown]

Short title: SE	KEINE
UOB ethics number: ERN_	3117

Usual duration of treatment	Prucalopride can be administered long- term, although the efficacy of the drug in the treatment of constipation has only been established up to 3 months.
Where will drug/substance be sourced from?	The drug will be sourced from an approved supplier in the form of 1mg film-coated tablets.
Where will drug/substance be stored?	Prucalopride will be stored in a locked drug cabinet in Birmingham and Solihull Mental Health Trust Pharmacy. It will be stored at room temperature in this locked cupboard, which is suitable for drug storage.
How will drug/substance be dispensed?	Prucalopride will be dispensed by a study clinician.
How will the drug/substance be prepared by the researchers for use in this study?	Prucalopride will be encapsulated by trained support staff using the Standard Operating Procedure of NHS Scotland Pharmaceutical 'Specials' Service

#### 9.2 Placebo

Name of drug/substance to be used	Lactose Placebo
Formulation and route of administration for study	Placebo will be encapsulated in opaque capsules.
Dose and route of administration for study	One capsule taken orally, daily for 2 days; 2 capsules for remaining 5-8 days
Duration of treatment for study	Seven to ten days
Licence status of this drug/substance	N/A
Usual Indication	N/A
Usual Dose	N/A
Usual duration of treatment	N/A
Where will drug/substance be sourced from?	Placebo will be sourced from an approved supplier of NHS Scotland Pharmaceutical 'Specials' Service
Where will drug/substance be stored?	Placebo will be stored in a locked drug cabinet in the Birmingham and Solihull Mental Health Trust (BSMHFT) Pharmacy. It will be stored at room temperature in this locked cupboard, which is suitable for drug storage.
How will drug/substance be dispensed?	Placebo will be dispensed by a study clinician.
How will the drug/substance be prepared by the researchers for use in this study?	Placebo will be encapsulated by trained staff of NHS Scotland Pharmaceutical 'Specials' Service according to their SOP.

11. Safety Measures and Contacts During the Study

Participants will be closely monitored for serious mental illness when in the study. Symptomatology of participants will be tracked using questionnaires for psychosis, mood and anxiety (PLE, PHQ-9, GAD-7). [name] and Professors [name] and [name] have experience in the management of acute mental illness including transition to psychosis. Participants will also be asked to provide the contact details of their GP or other health care professional who can be informed about their participation in the study.

Similarly, relevant medical history will be deemed as that reported during the baseline screening assessment.

The dose of prucalopride will be titrated with 1mg for 2 days, followed by 2x1mg for the remainder or the study. All participants will received a check-in from the study team at day 2 and 4. If participants are experiencing side effects at the day 2 check-in (before potential dose escalation) or day 4 check-in (after potential dose escalation), a clinician on the study team will be contacted to discuss the best management plan for the participant. Dose escalation for prucalopride in this manner has been found to be very well tolerated, including in participants who are antidepressant – naïve (as determined by the PROGRESS study). Side effects will be formally checked at baseline and study end using the side effects checklist.

Reports of adverse events which are reported by the participant and/or study team member(s) as possibly having been caused by the study activities (e.g. distress during interview, or because of interaction with study team) will include separate individual assessment of seriousness and causality. We will also report these as required using the Yellow Card Scheme: www.mhra.gov.uk/yellowcard.

Adverse events and serious adverse events will be recorded, investigated, and reported as per the Standard Operating Procedure (UoB SOP: ADVERSE EVENT REPORTING, V2.0, 20.1.2023).

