#### Study Visit 2 (baseline and randomisation) & Study Visit 3 (Follow-up after 7-10 days medication):

All procedures are the same for visit 2 and 3 unless otherwise specified

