#### 1) Questionnaires:

- -7-item Psychotic Like Experiences (PLE) questionnaire [17]
- -Perceived Deficits Questionnaire (PDQ) subjective cognition scale
- -Patient Health Questionnaire (PHQ-9) depression scale

UNIVERSITYOF BIRMINGHAM

-Generalised Anxiety Disorder Assessment (GAD-7) anxiety scale

- -Snaith-Hamilton Pleasure Scale (SHAPS) anhedonia scale
- -Side effects checklist
- 2) Neurocognitive battery suitable for repeated measures known to be sensitive to 5-HT4 agonism in previous studies
- -Auditory Verbal Learning Task (AVLT)
- -Working memory (N-back)
- -Facial Expression Recognition Task (FERT)
- -Probabilistic Instrumental Learning Task (PILT)
- 3) MRI / MRS scan (as in (17)) including physiological assessment (heart rate variability)
- -Structural (T1) (Baseline visit only)
- -Resting state fMRI scan
- -Magnetic Resonance Spectroscopy (MRS)
- 5) **Blood samples** (pre- and on-drug/placebo samples): for preparation/storage and analysis of immune cell phenotypes/biomarkers and prucalopride levels
- A blood sample of approximately 20ml (1.25 tablespoons) will be collected to measure: IL-1b, IL-6, IL-10, TNFa, IFNg, BDNF, S100B and SuPAR and prucalopride levels
- Blood samples will be collected by a qualified phlebotomist / trained clinician at two separate study time points (baseline and after 7-10 days' of medication).
- The intention behind taking the blood samples is to process them for the purpose of analysis of subcellular components (all biomarkers and drug levels will be analysed from plasma / serum).
- After collection, blood samples will be transported to [name] Laboratory group based in the College of Medical and Dental Sciences, Institute for Clinical Sciences at the University of Birmingham on the same day for preprocessing and storage as per their Standard Operating Procedures. This will include the use of the HBRC for storage of cellular material for analysis in future studies. Pre-processing to cellular / acellular components and transfer of cellular material to the HBRC will occur within one week of collection. After pre-processing, plasma and serum will be stored in [name]' Laboratory until required for analysis.
- 6) Optional Microbiome analysis (collection to take place at home):

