#### 17.1 Analysis plan outline:

#### Questionnaire data

Comparison of ANOVA or linear mixed models to compare groups (prucalopride versus placebo) over two time points (baseline versus follow up) on:

- 1) Questionnaires of psychotic-like experiences (PLE), perceived cognitive deficits (PDQ), mood and anxiety (PHQ-9, GAD-7, SHAPS, visual analogue scale of state affect)
- 2) Side effect checklist

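### The side effects checklist is given only before drug and at day 7-10, so early, transient side effects are not measured with the same instrument in both arms, although everyone is already contacted on days 2 and 4

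*Protocol*

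**What the plan says.** **Dose steps.** In section 10 (table headed 9.1), prucalopride is given as "1mg oral dose daily for 2 days, then 2x1mg oral dose daily for 5-8 days". The placebo table (9.2) mirrors the capsule count: "One capsule taken orally, daily for 2 days; 2 capsules for remaining 5-8 days".

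**Contacts during treatment.** Section 11 states: "All participants will received a check-in from the study team at day 2 and 4". It places the first contact before the possible step and the second after it. If a participant reports side effects at either contact, "a clinician on the study team will be contacted to discuss the best management plan for the participant". No questionnaire or structured record is named for these contacts.

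**Formal measurement.** Section 11 continues: "Side effects will be formally checked at baseline and study end using the side effects checklist". This agrees with section 8.1, which puts the checklist among the Visit 2 and Visit 3 questionnaires, and with the schedule in section 8.2, which marks side effects at baseline and follow-up and has no row for the two contacts.

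**Analysis.** For the questionnaires, including the side effect checklist, section 17.1 plans to "compare groups (prucalopride versus placebo) over two time points (baseline versus follow up").

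**Other safety recording.** The last paragraph of section 11 sends adverse events and serious adverse events to the sponsor's reporting SOP. Sections 15.1 and 15.2 have them reviewed by the PI and at study management meetings every three to four months.

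**The concern.** The protocol places its two contacts on either side of the dose step, which suggests that it sees these days as the ones when side effects may need attention. Yet the instrument used to compare the arms is applied only before the first dose and at the end of treatment. A side effect that starts in the first days and has settled by Visit 3 may leave no trace in that comparison. The between-arm result would then mainly describe what is present after 5 to 8 days at the higher level.

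A later SAP can refine how the data are analysed, but it cannot supply checklist scores that were never collected. Collection times are fixed in this document, so this is the place to change them.

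**Working it through.** **Inputs**
- First step: 2 days. Second step: 5 to 8 days (section 10).
- Checklist: Visit 2, before drug, and Visit 3, after 7 to 10 days of medication (sections 8.1, 8.2 and 11).
- Contacts: days 2 and 4, all participants (section 11).
- Assumptions: the first dose is day 1, and Visit 3 falls on the last dosing day. If it falls a day later, each interval below grows by one day.

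**Reproducing the plan's treatment length.** 2 + 5 = 7 and 2 + 8 = 10 days, which matches the seven to ten days in section 10. The second step begins on day 3.

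**Time from each early point to the only on-drug checklist**

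| Early point | Visit 3 at day 7 | Visit 3 at day 10 |
|---|---|---|
| Day 2 contact | 7 − 2 = 5 days | 10 − 2 = 8 days |
| Start of second step (day 3) | 7 − 3 = 4 days | 10 − 3 = 7 days |
| Day 4 contact | 7 − 4 = 3 days | 10 − 4 = 6 days |

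**Number of checklists on drug.** Now 1 (Visit 3), with none during the first step. With the day 2 and day 4 contacts added: 1 + 2 = 3, with one on each side of the step.

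**What the Visit 3 form can capture.** The documents do not give its recall period. There are two cases:
- If it asks about current symptoms, effects that have already resolved are missed.
- If it asks about the whole period since baseline, resolved effects can be reported, but from memory over up to 10 days and probably without separating the two dose steps.

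**Illustration only.** The documents give no incidence of side effects and no rate at which they settle. The rates here are assumptions: 10% with placebo, 30% to 60% with drug in the early days, and all, half or a quarter of the excess still present at Visit 3. Take n = 18 per arm (section 16.1), a two-sided 5% test and the normal approximation:

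power = Φ[(|p1 − p2| − 1.96·√(2·p̄(1 − p̄)/n)) / √((p1(1 − p1) + p2(1 − p2))/n)], where p̄ is the mean of p1 and p2.

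For 50% against 10%: (0.40 − 1.96 × 0.1528) / 0.1374 = 0.73, so power is about 77%. If half the excess remains, the comparison is 30% against 10%: (0.20 − 1.96 × 0.1333) / 0.1291 = −0.47, so power is about 32%.

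| Assumed early rate on drug | Measured when present | Half the excess remains | A quarter remains |
|---|---|---|---|
| 30% | 32% | 13% | 7% |
| 40% | 55% | 21% | 9% |
| 50% | 77% | 32% | 13% |
| 60% | 92% | 43% | 17% |

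The table shows the direction of the effect if the Visit 3 form asks about current symptoms only. The conclusion does not rest on it.

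**The case against.** The strongest case against is that the plan is consistent on this point and that the measure is peripheral. Sections 8.1, 8.2, 11 and 17.1 agree with one another. Section 5.2 says that establishing or comparing the drug's safety is outside the study's aims, and section 8.5 does not list tolerability among the outcomes. This stands, and it limits the point to an optional improvement.

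A reader might infer more than the documents support:
- **That early side effects are certain to be lost.** They are not. The recall period is unstated, and a form that looks back over the whole period could capture some of them.
- **That adverse event recording covers only events thought to be caused by study activities.** That restriction belongs to the sentence on separate assessment of seriousness and causality. The closing paragraph of section 11 has no such limit, so a symptom mentioned on day 2 or 4 has a route into the record.
- **That the trial fails to test the statement that this escalation is well tolerated.** Section 11 credits that statement to an earlier study. It is background here and not a hypothesis.
- **That the check-in reports will go unanalysed.** Section 17.1 is an outline, and a SAP may tabulate adverse events. What a SAP cannot do is create same-instrument scores for days 2 and 4.

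A further objection is that asking about specific symptoms twice more before Visit 3 could encourage treatment guessing, and section 12 lists accidental unblinding as a risk. This stands in part. The added risk should be small, because the contacts already deal with side effects.

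**Conclusion.** The point holds as a limited one. Early, transient side effects are not measured systematically with the same instrument in both arms. They do not enter the outlined comparison unless the Visit 3 form covers the whole treatment period, and then they rest on recall and probably cannot be assigned to a dose step.

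In size, there is one on-drug checklist, 4 to 7 days after the step, where three could be had at contacts already planned. No figure for lost information can be drawn from the documents. That early days matter most for side effects is an inference from where the protocol places its contacts, not a result it reports. Since adverse events are recorded in any case and tolerability is not a listed outcome, the consequence is modest and the priority low.

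**What to change.** 1. Give the same side effects checklist at the existing day 2 and day 4 contacts, in both arms, and record it in REDCap or the eCRF.
2. Add the two occasions to the side-effect comparison in section 17.1, for example as worst on-treatment score and as score by time.
3. State the checklist's recall period for each occasion.
4. Add the two contacts to the schedule in section 8.2 and amend the sentence in section 11 to match.

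The cost is a few minutes per contact for participant and staff, a short protocol edit, and a small possible increase in treatment guessing. The end-of-study guess question already planned in section 9 can help assess that increase. The change concerns data collection only and leaves dosing and management rules as they are.
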